7.1 Overview of Patient Assessments

After an initial screening period of up to 28 days (4 weeks), patients will be treated with FPA144 every 2 weeks (\pm 3 days) in 28-day cycles, and FPA144 will be administered as a 30-minute infusion. All time points of assessments should be completed in the timeframe stated.

Assessments performed prior to the patient signing the informed consent are acceptable only if confirmed to have been standard of care.

The schedule of detailed patient assessments is shown in [Appendix 1](#) and [Appendix 2](#).

Instructions for the sampling and processing of PK and immunogenicity data are described in a separate, protocol-specific laboratory manual.

7.2 Study Assessments and Procedures by Visit

7.2.1 Pre-Study Period (*Parts 1B and 2*)

Study eligibility for Part 1B and Part 2 includes analysis of either archived or recently obtained tumor tissue for evaluation of FGFR2b overexpression and *FGFR2* amplification. Potential patients may elect to consent for this tumor tissue analysis by a third party laboratory in the United States at any time prior to enrollment into the study.

In Part 1B, approximately 3 gastric cancer patients may be enrolled at each dose level, whose tumor tissue may be tested retrospectively. The Sponsor and Investigators may elect to enroll up to an additional 3 patients per dose level whose tumors overexpress FGFR2b.

In Part 2, those patients whose tumors are documented to have FGFR2b overexpression will subsequently be given the opportunity to consent to full study participation, and will undergo in-clinic screening to ensure the eligibility criteria are met.

7.2.2 Screening Period (*Day –28 to Day 0*)

Written, signed informed consent must be collected prior to any study-specific procedures.

Patients who have fully consented to participation in the study will undergo screening assessments within 28 days (4 weeks) prior to administration of the first infusion of FPA144 (unless otherwise stated). To determine if the patient meets all the inclusion criteria and does not violate the exclusion criteria, the following procedures will be performed:

- Tumor tissue for central FGFR2b expression testing

Note: This requirement is mandatory for Part 1B and Part 2 of the study, and may be done at any time prior to enrollment. Tumor tissue analysis for Part 1B may be done prospectively or retrospectively. Tumor tissue analysis will be encouraged for patients enrolled in Part 1A, for retrospective analysis. *FGFR2* amplification testing may be performed either prospectively or retrospectively for patients in Part 1B, but will only be performed retrospectively for patients enrolled in Part 2.

- Complete medical and disease history

- Demographic and baseline characteristics
- Vital signs (sitting blood pressure, pulse, respiration, and body temperature [°C] after 5 minutes rest)
- Complete physical examination, including weight, and height
- Comprehensive ophthalmologic exams including fundoscopic and slit lamp exam, ocular coherence tomography (OCT), determination of intraocular pressure, visual acuity, completion of fluorescein staining score form, and review of ocular/visual symptoms.
- ECOG performance status evaluation
- 12-lead ECG (required at screening, and if clinically indicated during the study)
- Document prior and concurrent medications
- Hematology (hemoglobin, hematocrit, white blood cell [WBC] and differential [with ANC], and platelet count). Blood will be analyzed by a local laboratory
- Serum chemistry (total protein, albumin, creatinine, BUN or urea, uric acid, total bilirubin, alkaline phosphatase (ALP), ALT, AST, lactate dehydrogenase (LDH), glucose, globulin, phosphate, calcium, sodium, potassium, magnesium, chloride, carbon dioxide (CO₂ [bicarbonate]), total cholesterol, creatinine, and direct bilirubin. Blood will be analyzed by a local laboratory
- Urinalysis (includes dipstick for protein, glucose, blood, pH, and ketones)
- Serum pregnancy test (beta-human chorionic gonadotropin [β -HCG]), ≤ 5 days prior to Cycle 1 Day 1, for women of childbearing potential
- Radiological imaging/tumor assessments: Tumor assessments should consist of clinical examination and appropriate imaging techniques (preferably CT scans with appropriate slice thickness per RECIST v1.1); other assessments (MRI, X-ray, PET, and ultrasound) may be performed if required. The same methods used to detect lesions at baseline are to be used to follow the same lesions throughout the clinical study. CT assessments are to be performed within 28 days prior to the first infusion of FPA144. Radiological assessments performed as part of the patient's standard of care within 28 days of the first study infusion do not need to be repeated if the documentation of results is provided and is adequate for an assessment.
- Mandatory as feasible biopsy collection (at least 24 hours prior to dosing) for patients enrolled in Part 2

Note: A protocol-specific Patient Enrollment Number Assignment Form must be submitted to the Sponsor (or designee) to confirm patient eligibility prior to initiation of study treatment and assignment of a patient enrollment number.

7.2.3 Treatment Allocation (Dosing Assignment)

This is an open-label study. Enrollment numbers will be faxed or emailed to the Investigator (or designee). The Sponsor or designee will maintain records of the number of patients treated

within a specific cohort and will determine to which treatment cohort newly enrolled patients will be assigned.

7.2.4 Cycle 1, Day 1 (*Parts 1A, 1B, and 2*)

The following procedures will be performed:

- Prior to FPA144 infusion (within ≤ 72 hours unless otherwise stated):
 - Verification of eligibility
 - Update medical and disease history to capture any changes from screening
 - AE reporting, if applicable, and review of concomitant medications
 - Vital signs (sitting blood pressure, pulse, respiration, and body temperature [$^{\circ}\text{C}$] after 5 minutes rest)
 - Limited physical examination including weight and oral exam
 - Clinical safety labs (hematology results must be available prior to dosing)
 - Serum β -hCG (evaluated by local laboratories) will be performed ≤ 5 days prior to the first dose of FPA144 only on women of childbearing potential
 - Urinalysis
 - Blood sample for immunogenicity testing ≤ 4 hours prior to dosing of FPA144
 - Blood sample for PK ≤ 4 hours prior to dosing of FPA144
 - Optional blood sample for FCGR polymorphism testing
 - Blood-based biomarker sample collection in all patients enrolled in Part 2 as outlined in [Appendix 2](#)
- Study drug administration:
 - Administer FPA144, by IV infusion over approximately 30 minutes
- Post FPA144 administration:
 - Post-dose Vital signs (sitting heart rate, blood pressure, respiration, and body temperature [$^{\circ}\text{C}$] after 5 minutes rest) at the following time points relative to the start of the infusion:
 - ♦ 0.5 hours (within 5 minutes after end of infusion), + 1 hour (± 5 minutes), 2 hours (± 5 minutes), and 4 hours (± 5 minutes) from start of infusion.
 - AE reporting and review of concomitant medications, if applicable
 - PK sample collection, at the following time points *relative to the start of the infusion*:
 - ♦ **Part 1A:** 0.5 hours (within 5 minutes after end of infusion), + 1 hour (± 5 minutes), 2 hours (± 5 minutes), 4 hours (± 5 minutes), and 8 hours (± 5 minutes) from start of infusion.

- ◆ **Part 1B:** 0.5 hours (within 5 minutes after end of infusion), + 1 hour (± 5 minutes), and 4 hours (± 5 minutes) from start of infusion.
- ◆ **Part 2:** PK sample collection at 0.5 hours (within 5 minutes after end of infusion), + 1 hour (± 5 minutes), and 4 hours (± 5 minutes) from start of infusion as outlined in [Appendix 2](#).

7.2.5 Cycle 1, Day 2 (*Part 1A and B only*)

- Vital signs (sitting heart rate, blood pressure, respiration and body temperature)
- PK sample collection at the following time point:
 - 24 hours (± 1 hour) from start of infusion on Day 1
- AE reporting, if applicable, and review of concomitant medications

7.2.6 Cycle 1, Day 4 (*Part 1A and 1B only*)

- Vital signs (sitting heart rate, blood pressure, respiration and body temperature)
- PK sample collection at the following time point:
 - 72 hours (+24 hour) from start of infusion on Day 1
- AE reporting, if applicable, and review of concomitant medications

7.2.7 Cycle 1, Day 8 (*Parts 1A, 1B and 2*)

Study patients will return to the study center on Day 8 (± 2 days). No treatment will be administered.

The following assessments will be completed:

- Vital signs (sitting blood pressure, pulse, respiration, and body temperature [$^{\circ}\text{C}$] after 5 minutes rest)
- Limited physical examination including oral exam
- Clinical safety labs
- Blood sample for PK
- AE reporting, if applicable, and review of concomitant medications

7.2.8 Cycle 1, Day 15 (*Parts 1A, B, and 2*)

Study patients will return to the study center on Day 15 and the following assessments will be completed.

- Prior to FPA144 infusion (within ≤ 72 hours unless otherwise stated):
 - Vital signs (sitting blood pressure, heart rate, respiration, and body temperature [$^{\circ}\text{C}$] after 5 minutes rest)

- Limited physical examination including weight and oral exam
- Clinical safety labs (hematology results must be available prior to dosing)
- Blood sample for PK, ≤ 4 hours prior to dosing of FPA144
- AE reporting, if applicable, and review of concomitant medications
- Mandatory as feasible biopsy collection for patients enrolled in Part 2 only, at **either**:
- 15 days on-treatment (within 7 days prior to Cycle 1 Day 15 and at least 24 hour prior to dosing)

Or

- 29 days on-treatment (within 7 days prior to Cycle 2 Day 1 and at least 24 hour prior to dosing).
- Study drug administration:
 - Administer FPA144, by IV infusion over 30 minutes
 - Post FPA144 administration:
 - PK sample collection at 0.5 hours (within 5 minutes after end of infusion)
 - Post-dose Vital signs (sitting heart rate, blood pressure, respiration, and body temperature [$^{\circ}$ C] after 5 minutes rest) at the following time points relative to the start of the infusion:
 - ♦ 0.5 hours (within 5 minutes after end of infusion) and + 1 hour (± 5 minutes)
 - AE reporting, if applicable, and review of concomitant medications

7.2.9 End of Cycle 1 (Part 1A only)

For Part 1A patients, if at the end of Cycle 1 the Investigator determines that the patient may benefit from continued dosing with FPA144, entry into the Extended Treatment Period may be offered.

- If the patient is continuing onto the Extended Treatment Period (Cycle 2), proceed to procedures outlined in Section 7.2.10.
- If the patient does not qualify to receive further doses of FPA144, the patient will undergo procedures in an EOT visit (see Section 7.2.11).

7.2.10 Part 1A Extended Treatment/Part 1B and Part 2 Cycle 2 and Subsequent Cycles

Part 1A Extended Treatment may begin on Cycle 2, Day 1. Dosing will be discontinued if the patient experiences either disease progression or unacceptable toxicity.

At each infusion visit, patients are to remain at the study site after each administration of FPA144 until completion of all post-dose assessments for safety monitoring. The following assessments will be performed at each visit unless otherwise noted:

7.2.10.1 Cycle 2 and Subsequent Cycles, Day 1 and Day 15 (*Parts 1A, 1B, and 2*)

- Prior to each infusion of study drug:
 - Vital signs (sitting heart rate, blood pressure, respiration, and body temperature [°C] after 5 minutes rest)
 - Limited physical examination including oral exam
 - Weight on Day 1 of each Cycle (after Cycle 1, dose will be recalculated only if weight has changed >10% from Cycle 1, Day 1)
 - Comprehensive ophthalmologic exams including fundoscopic and slit lamp exam, ocular coherence tomography (OCT), visual acuity, completion of fluorescein staining score form, determination of intraocular pressure, and review of ocular/visual symptoms prior to Cycle 2 Day 1 only
 - Slit lamp exams (including completion of fluorescein staining form) without OCT every 6 weeks through Cycle 6, Day 15 (prior to Cycle 3, Day 15; Cycle 5, Day 1; Cycle 6, Day 15), and every 12 weeks starting at Cycle 6, Day 15. Continue every 6–8 weeks if the patient has any persistent corneal findings
 - Note:* Refer for additional comprehensive ophthalmologic evaluation at any time if patient complains of photophobia, vision changes, or eye pain
 - ECOG performance status evaluation (Cycle 2 Day 1, then Day 1 of every subsequent Cycle)
 - Clinical safety labs (hematology results must be obtained prior to dosing)
 - Blood sample for PK (≤ 4 hours pre-dose)
 - Day 1 Cycles 2-5 and starting at Cycle 5, blood samples will only be collected every other Cycle on Day 1 (Cycle 5, 7, and 9 etc...)
 - Blood sample for immunogenicity (≤ 4 hours pre-dose).
 - Day 1 Cycles 2-5 and starting at Cycle 5, blood samples will only be collected on Day 1 of every other Cycle (Cycles 5, 7, and 9 etc...)
 - Urinalysis Day 1 of each Cycle
 - Tumor assessment using the same physical or radiologic parameter(s) used to evaluate baseline tumor measurements are to be done every 6 weeks from the first dose for 24 weeks (within 7 days prior to the start of Cycle 2 Day 15, Cycle 4 Day 1, Cycle 5 Day 15, Cycle 7 Day 1), then approximately every 12 weeks thereafter.
 - Mandatory as feasible biopsy collection for patients enrolled in Part 2 only, at **either**:
 - 15 days on-treatment (within 7 days prior to Cycle 1 Day 15 and at least 24 hour prior to dosing)

Or

- 29 days on-treatment (within 7 days prior to Cycle 2 Day 1 and at least 24 hour prior to dosing).
- Optional biopsy (after discussion with the Sponsor) for consenting patients enrolled in Part 2 who responded to treatment (within 14 days post tumor assessment)
- Optional exploratory archival tumor tissue analysis for consenting patients enrolled in Part 2
- Blood-based biomarker sample collection every 6 weeks from the first dose for 24 weeks (prior to Cycle 2 Day 15, Cycle 4 Day 1, Cycle 5 Day 15, Cycle 7 Day 1), and then approximately every 12 weeks thereafter from patients enrolled in Part 2 as outlined in [Appendix 2](#)
- AE reporting, if applicable, and review of concomitant medications
- Study drug administration:
 - Administer FPA144, by IV infusion over 30 minutes
- Post study drug administration:
 - Post-dose vital signs (sitting heart rate, blood pressure, respiration, and body temperature [°C] after 5 minutes rest) at the following time points relative to the start of the infusion:
 - ♦ 0.5 hours (after the end of infusion) and +1 hour (±5 minutes)
 - PK sample collection at 0.5 hours (from start of infusion, within 5 minutes after end of infusion)
 - ♦ Day 1 Cycles 2-5 and starting at Cycle 5, blood samples will only be collected on Day 1 of every other Cycle (Cycle 5, 7, and 9 etc...)
 - AE reporting, if applicable, and review of concomitant medication

7.2.11 End-of-Treatment Visit or Early Termination

Patients will return to the study center approximately 28 (± 3) days after their last infusion of FPA144, or in the event a patient discontinues prematurely from the study.

The following assessments will be performed at the EOT visit:

- Vital signs (sitting pulse, blood pressure, respiration, and body temperature [°C] after 5 minutes rest)
- 12-lead ECG
- Limited physical examination including oral exam
- ECOG performance status evaluation

- Comprehensive ophthalmologic exams including fundoscopic and slit lamp exam, ocular coherence tomography (OCT), visual acuity, intraocular pressure, completion of fluorescein staining score form, and review of ocular/visual symptoms if at least 6 weeks since the previous ophthalmologic exams.
- Clinical safety labs
- Blood sample for PK
- Blood sample for immunogenicity
- Serum β -hCG (evaluated by local laboratories) in women of child-bearing potential
- Blood- based biomarker sample collection from patients enrolled in Part 2 as outlined in [Appendix 2](#)
- Urinalysis
- Tumor assessment using the same physical or radiologic parameter used to evaluate baseline tumor measurements. *(This scan can be omitted if the last scan was performed <6 weeks prior to EOT visit or if tumor progression was previously determined.)*
- Optional biopsy (after discussion with the Sponsor) for consenting patients enrolled in Part 2 who progressed, (28 [\pm 7] days, post last infusion of FPA144 visit only)
- AE reporting, if applicable, and review of concomitant medications

8. Statistical Methods

Before database lock, a separate statistical analysis plan (SAP) will be finalized, providing detailed methods for the analyses outlined below.

Any deviations from the planned analyses will be described and justified in the final integrated study report.

8.1 Study Patients

8.1.1 Disposition of Patients

The number and percentage of patients entering and completing each phase (e.g., Screening, Cycle 1, and Extended Treatment Period) of the study will be presented. Reasons for withdrawal will also be summarized.

8.1.2 Protocol Deviations

A summary of the number and percentage of patients with major protocol deviations by type of deviation will be provided. Deviations will be defined in the SAP prior to database lock.

8.1.3 Analysis Populations

The following analysis populations are defined for the study:

- Safety Population—all patients who have received any portion of at least one dose of FPA144.
- DLT-Evaluable Population—all patients enrolled into Part 1A of the study who received at least 2 doses of FPA144 and completed Cycle 1 of treatment, or who experienced a DLT in Cycle 1.
- PK-Evaluable Population—all patients who have received at least one dose of FPA144 and have had adequate PK assessments drawn for determination of the PK profile. Adequacy will be determined on a case-by-case basis and will be assessed prior to analysis of the blood samples.
- Efficacy-Evaluable Population—all patients who met eligibility criteria, received at least 1 dose of FPA144, have measurable tumor lesions at baseline, and have at least 1 post-Baseline disease assessment.

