Patients enrolled in Part 1(A and B) or Part 2 of the study may continue treatment with FPA144 in 28-day cycles until disease progression, intolerable toxicity, patient or physician decision to discontinue, death, or termination of the study. Responding patients who discontinue treatment while still in response (CR, PR or SD) should get follow-up scans at 12-week intervals to determine the duration of response, unless other anticancer therapy is started.

All patients should return to the clinic for end-of-treatment (EOT) assessments irrespective of whether a patient is withdrawn or withdraws at a planned visit or mid-cycle.

During Part 1(A and B) and Part 2, AEs will be assessed as outlined in Section [6.2.1.1](#) below.

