4.2 Inclusion Criteria for Study Participation

Patients enrolling into Part 1(A and B) or Part 2 must meet *all* of the following inclusion criteria:

1. Understand and sign an Institutional Review Board/Independent Ethics Committee-approved informed consent form prior to any study-specific evaluation
2. Life expectancy of at least 3 months
3. ECOG performance status of 0 to 1
4. Age ≥ 18 years at the time the informed consent form is signed except for the patients in Taiwan, where the patient's age must be ≥ 20 at the time the informed consent form is signed
5. In sexually-active patients (i.e., females of childbearing potential, who have not undergone menopause as defined by 12 consecutive months of amenorrhea or had a permanent sterilization procedure and males, who have not had a permanent sterilization procedure), willingness to use 2 effective methods of contraception, of which one must be a physical barrier method (condom, diaphragm, or cervical/vault cap) until 6 months after the last dose of FPA144. Other effective forms of contraception are permanent sterilization (hysterectomy and/or bilateral oophorectomy, or bilateral tubal ligation with surgery, or vasectomy) at least 6 months prior to Screening. Female patients of childbearing potential must be on stable oral contraceptive therapy or intrauterine or implant device for at least 90 days prior to the study, or abstain from sexual intercourse as a way of living
6. Adequate hematological and biological function, confirmed by the following laboratory values:
 - a) Bone marrow function
 - ♦ $ANC \geq 1.5 \times 10^9/L$
 - ♦ Platelets $> 100 \times 10^9/L$
 - ♦ Hemoglobin ≥ 9 g/dL
 - b) Hepatic function
 - ♦ AST and ALT ≤ 3 x upper limit of normal (ULN); if liver metastases, then ≤ 5 x ULN
 - ♦ Bilirubin ≤ 1.5 x ULN
 - c) Renal function
 - ♦ Serum creatinine ≤ 1.5 x ULN
7. Tumor tissue, must be available for determination of FGFR2b overexpression (*optional for Part 1A patients*)

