6.1 Tumor Response Parameters

Tumor assessments will be performed at Screening (within 28 days prior to first dose), then every 6 weeks from the first dose, for 24 weeks, and then every 12 weeks thereafter. Tumor assessments should be completed within 1 week prior to start of the dose when re-imaging is scheduled. All patients should have tumor response parameters assessed at the EOT visit unless a tumor assessment has been performed within the previous 6 weeks.

Response will be evaluated using RECIST v1.1 for measurable disease (*required for Part 2*). A response (complete or partial) to treatment must be confirmed 4–6 weeks later. Subsequent tumor assessments will be performed using the same physical, biomarker, or radiological parameter(s) used to measure the tumor at baseline.

Progressive disease is defined as the appearance of one or more of the following as described in RECIST v1.1 ([Eisenhauer 2009](#)):

- For patients with measurable disease, at least a 20% increase in the sum of diameters of target lesions, taking as reference the smallest sum on study (this includes the baseline sum if that is the smallest on study). In addition to the relative increase of 20%, the sum must also demonstrate an absolute increase of at least 5 mm.
- Unequivocal progression of currently or previously non-measurable lesions
- The appearance of one or more new lesions
- Development of clinical signs or symptoms which, in the opinion of the Investigator, indicate clinically significant disease progression

Note: Tumor assessments performed as part of the patient's standard of care within 28 days (4 weeks) of the first dose of FPA144 do not need to be repeated during screening.

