8.2 General Considerations

Data collected in this study will be presented using summary tables and patient data listings. Continuous variables will be summarized using descriptive statistics, specifically the mean, median, standard deviation (SD), minimum, and maximum. Categorical variables will be summarized by frequencies and percentages.

The statistical and analytical plans presented below summarize the more complete plans to be detailed in the statistical analysis plan (SAP). A change to the data analysis methods described in the protocol will require a protocol amendment only if it alters a principal feature of the protocol. The SAP will be finalized prior to database lock. Any changes to the methods described in the final SAP will be described and justified in the clinical study report.

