8.5 Analyses of Tumor Response

Patients will be classified according to their best overall tumor response (complete response [CR], partial response [PR], stable disease [SD], or progressive disease [PD]). Frequencies, proportions, and exact 95% CI of patients, when appropriate, stratified by their best overall tumor response will be calculated. Patients with a best overall tumor response of CR or PR with duration of at least 4 weeks (28 days) will be further classified as having an objective tumor response. Listing of patients with an objective tumor response will be presented.

Duration of response will be calculated as the number of days from the first documentation of overall response (CR or PR) to the first documentation of disease progression or death, whichever comes first. Patients who are alive and progression-free at the time of data analysis will be censored at the time of their last assessment for tumor response.

Duration of stable disease will be calculated from Cycle 1, Day 1.

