8.7 Efficacy Analysis

Efficacy analyses will be descriptive. The overall response rate will be summarized with frequencies and percentages. The duration of response for CR and PR patients will be summarized with descriptive statistics (N, mean, standard deviation, median, minimum, and maximum) as well as categorically. Response and duration of response will be determined using RECIST v1.1. Kaplan-Meier methodology will be used to summarize duration of response and PFS.

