8.10 Determination of Sample Size

Three patients per dose group, with a sample size increase to 6 in the case of DLT, is generally accepted as adequate to determine the safety of escalating doses of novel oncologic drugs. If a DLT is observed in 1 of 3 patients, then 3 additional patients will be enrolled at that same dose level. Dose escalation will continue until 2 of 3–6 patients treated at a dose level experience a DLT. The maximum tolerated dose (MTD) is defined as the maximum dose at which < 33% of patients experience a DLT during Cycle 1. After the MTD is determined, additional gastric cancer patients may be recruited at that dose level to further characterize the safety, PK, pharmacodynamics, and preliminary efficacy of FPA144.

In Part 1B, up to 30 patients with gastric cancer with or without FGFR2b overexpression, in the presence or absence of *FGFR2* amplification may be enrolled to explore preliminary long-term safety and PK.

In each of the Part 2 gastric cancer cohorts (Cohorts A, C, D, and E), approximately 30 gastric cancer patients with ranges of FGFR2b overexpression scores (IHC 3+ \geq 10%; IHC 0; IHC 2+ \geq

10% tumor membrane staining **and/or** IHC 3+ < 10%; IHC 1+ **and/or** IHC 2+ < 10%) will be enrolled and treated to further characterize safety and preliminary efficacy. For each cohort, a response rate of $\geq 20\%$ would be considered clinically meaningful. To ensure adequate efficacy, an interim analysis may be performed (with the assumption that a response rate of $\leq 5\%$ would be of no interest in the first stage). Assuming a significance level of 5% and 80% power (Table 5), the required sample size is 29 evaluable patients per cohort. The Sponsor may choose to suspend enrollment if no confirmed response (CR or PR) is observed after the first 10 evaluable patients have either received at least 4 cycles of therapy or have had disease progression, as it is unlikely the response rate would be 20% or more. If a full cohort of 30 patients is enrolled for a group, the precision of the 95% confidence interval for the response rate is within 18%.

Table 6: Parameters of Simon’s 2-stage Design

Targeted Response Rate	Response Rate of No Interest	Overall Sample Size	Sample Size at Stage I	Responses to go to Stage II	Number of Overall Responses
20%	5%	29	10	≥ 1	≥ 4

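### The only efficacy set requires a post-baseline assessment and no ORR denominator is named; if ORR uses that set, leaving out never-assessed treated patients raises it slightly, and this is cheap to avoid.

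*Combined protocol and SAP*

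**What the plan says.** Section 8.1.3 lists four populations: Safety, DLT-Evaluable, PK-Evaluable and Efficacy-Evaluable. Only the last is for efficacy. Its members must have met eligibility, received a dose, and "have measurable tumor lesions at baseline, and have at least 1 post-Baseline disease assessment".

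Section 8.5 sorts patients by best response into "complete response [CR], partial response [PR], stable disease [SD], or progressive disease [PD"]) and promises proportions with exact 95% intervals. It has no category for a patient who was never assessed. Section 8.7 adds only this on the rate: "The overall response rate will be summarized with frequencies and percentages". Neither section names a population, although Section 8.3 does so for baseline characteristics and Section 8.6 for safety.

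Section 8.10 states that "the required sample size is 29 evaluable patients per cohort", without tying the word evaluable to Section 8.1.3 or naming it as the ORR denominator. Detailed methods are left to a separate plan: "The SAP will be finalized prior to database lock" (Section 8.2). That plan is not in the supplied text.

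**The concern.** A treated patient with no post-baseline assessment cannot be a confirmed responder. Leaving such patients out of the denominator therefore lowers the denominator and never the numerator. They are likely to include patients who died or deteriorated early, so part of the reported rate would reflect early loss and not drug activity. Part 2 has no control arm, so a reader will judge the percentage by itself.

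What is at stake is limited. ORR by tumor type is a secondary objective (Section 2.2), and Section 8.7 makes the efficacy analyses descriptive.

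**Working it through.** **1. The plan's own design.** Inputs from Section 8.10 and Table 6: rates of 5% and 20%, at least 1 response in the first 10 patients, at least 4 in 29.

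P(pass) = Σ over x = 1 to 10 of Bin(10, x; p) × P[Bin(19, p) ≥ 4 − x]

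This gives 0.0468 at p = 0.05 and 0.8011 at p = 0.20, which agrees with the stated 5% and 80%. The figure of 29 evaluable patients is not in question.

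**2. The factor.** Let N be treated patients with measurable disease, x confirmed responders, k patients with no post-baseline assessment, and d = k/N. Section 6.1 requires confirmation of response 4–6 weeks later, so none of the k can be among the x.

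- Rate among treated = x/N
- Rate after dropping the unassessed = x/(N − k)
- Ratio = N/(N − k) = 1/(1 − d)

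The documents give no d, so 5% and 10% are assumptions:

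- 20% ORR: 0.20/0.95 = 21.1%; 0.20/0.90 = 22.2%
- 5% ORR: 0.05/0.95 = 5.3%; 0.05/0.90 = 5.6%

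**3. In patient counts, with exact (Clopper-Pearson) 95% intervals.** Cohort A is planned at about 20 (Section 4.1); a full cohort in Section 8.10 is 30. The responder counts are illustrative.

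| Treated | Responders | Unassessed | ORR after dropping them | Exact 95% CI | Width (points) |
|---|---|---|---|---|---|
| 20 | 4 | 0 | 4/20 = 20.0% | 5.7–43.7% | 38.0 |
| 20 | 4 | 1 | 4/19 = 21.1% | 6.1–45.6% | 39.5 |
| 20 | 4 | 2 | 4/18 = 22.2% | 6.4–47.6% | 41.2 |
| 30 | 6 | 0 | 6/30 = 20.0% | 7.7–38.6% | 30.9 |
| 30 | 6 | 1 | 6/29 = 20.7% | 8.0–39.7% | 31.7 |
| 30 | 6 | 2 | 6/28 = 21.4% | 8.3–41.0% | 32.7 |
| 30 | 6 | 3 | 6/27 = 22.2% | 8.6–42.3% | 33.7 |

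**4. The eligibility condition is separate.** An ineligible patient may have responded. From 6/30, dropping 3 ineligible patients of whom 1 responded gives 5/27 = 18.5%, a ratio of 0.926. Dropping 3 of whom none responded gives 6/27 = 22.2%. So the factor in step 2 applies only to the no-assessment exclusion, and d must not include ineligible patients.

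**5. Can d be taken as zero?** The first scheduled scan is at week 6. The end-of-treatment (EOT) visit is about 28 days after the last infusion (Section 7.2.11). Sections 6.1 and 7.2.11 waive the EOT scan if one was done in the previous 6 weeks, and neither says that the earlier scan must be post-baseline. For a patient who receives one dose, 42 − 28 = 14: a screening scan less than 14 days before that dose still falls within 6 weeks of EOT. Such a patient could leave without a post-baseline scan and without breaking the protocol. Deaths before the first scan and patients who do not return add to this.

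**6. Why the two-stage rule should stay as it is.** If 20% is the target among evaluable patients and unassessed patients were counted within the 29, the rate becomes 0.20(1 − d) = 0.19 or 0.18. The pass probability then falls from 80.1% to 76.8% or 73.0%.

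**The case against.** **The denominator is not stated, so the harm is conditional.** This stands. Section 8.5 speaks of proportions of patients and reserves objective response for a CR or PR lasting at least 4 weeks, so a treated patient with neither could be read as a non-responder. The pending SAP may settle it. Against that, only one set is labelled for efficacy, and Section 8.10 counts evaluable patients.

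**The protocol keeps d small.** This largely stands. Entry requires "Life expectancy of at least 3 months" (Section 4.2). Section 3.2 says "All patients should return to the clinic for end-of-treatment (EOT) assessments", and Section 6.1 says "All patients should have tumor response parameters assessed at the EOT visit", subject to the 6-week waiver. Section 6.1 also counts clinical deterioration as progression, and the set asks for a disease assessment, not specifically a scan. These limits reduce d but do not make it zero.

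**The treated-patient rate is recoverable.** In part. Section 8.1.3 defines the treated population and Section 8.5 promises a listing of responders, so someone holding the full report could form the ratio. A reader of the summary percentage could not.

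**Two stronger readings are tempting.** A reader might infer that ORR on this set always exceeds the treated rate by the factor 1/(1 − d). Step 4 shows that it need not, because ineligible patients are removed too. A reader might also infer that the two-stage decision is biased. The documents do not support that: Section 8.10 both sizes and applies the rule on evaluable patients, and does not say that its 5% and 20% are rates among all treated patients.

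**Conclusion.** The point holds as a minor, cheap improvement. The plan has one efficacy set, that set requires a post-baseline assessment, and nothing states the ORR denominator or how an unassessed patient is counted. On the inferred reading that ORR uses this set, the no-assessment exclusion can only leave ORR unchanged or raise it.

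The expected size is about 1 to 2 points on a 20% rate. This rests on an assumed d of 5% to 10% that the documents neither give nor rule out. Against the interval widths in step 3 the shift would not alter the interpretation of a cohort. It is nevertheless one-directional, so enrolling more patients would not average it out. Nothing here shows that a reported ORR is or will be inflated, and the gain from the change is confined to the descriptive ORR and its interval.

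**What to change.** In Sections 8.1.3, 8.5 and 8.7, and then in the SAP:

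- Make all patients who received any FPA144 and had measurable disease at baseline the main denominator for the reported ORR and its exact 95% interval. Because Part 2 entry requires measurable disease (Section 4.2.3), this is in effect all treated Part 2 patients. State that it includes treated patients later found ineligible.
- Add a 'not evaluable' best-response category, counted as non-response.
- Keep the Efficacy-Evaluable set as a supportive analysis, and report by cohort how many treated patients it excludes and why (no assessment, or ineligible).
- Leave the 10/29 two-stage rule on evaluable patients, and state beside it how many treated patients were not evaluable. The change should not be presented as altering that decision. Redefining the rule would cost power (step 6), and 12 Cohort A patients had already enrolled by the October 2016 cut-off (Section 1.7).

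The cost is one added population, the new category, and a sentence each in Sections 8.5 and 8.7, with no new data. The downsides are a slightly lower reported ORR and the inclusion of treated ineligible patients, whose effect can go either way. The headline ORR will also be on a different footing from the two-stage rule, which is why the not-evaluable count belongs beside that rule.
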